Evaluation of AI Cost Prediction Model to Enroll Patients in Complex Care Management Program

Analysis Plan

ID: IRB-24-0848

IRB Approved 6/12/2024

NCT ID: Not yet assigned

Document Updated March 31, 2025

Primary Outcome

Days alive and out of hospital (DAOH) at 120 days from randomization

Secondary Outcomes

- Days alive and out of hospital (DAOH) at 30 days from randomization
- Days alive and out of hospital (DAOH) at 90 days from randomization
- Days alive and out of hospital (DAOH) at 10 months from randomization
- Total healthcare expenditures at 10 months from randomization
- All-cause hospitalizations at 10 months from randomization
- All-cause emergency department visits at 10 months from randomization
- All-cause mortality at 10 months from randomization
- Ambulatory contact days out of home (days with a primary care or specialty care office visit, test, imaging, procedure, or treatment)

Exploratory Outcomes

- Cost prediction model performance over 22 months, as measured by area under the receiver operating characteristic curve. Observed healthcare expenditures for each month's control cohort will be measured over the subsequent 12 months after randomization (ie, 10 months of enrollment + 12 months of follow-up= 22 months), and compared to model-predicted healthcare expenditures. This analysis will only be conducted in the control group, as the intervention is designed to affect healthcare expenditures in the treatment group.
- Protocol fidelity over the 10 months of enrollment, measured by the proportion of patients randomized to the intervention who enroll in the complex care management program, and the proportion of patients randomized to the control who do not enroll in the complex care management program.
- Avoidable hospitalizations, defined as hospitalizations that could have been avoided through timely access to ambulatory care.
- Avoidable emergency department visits, defined as emergency department visits that could have been avoided through timely access to ambulatory care.

Analysis plan

The investigators will compare the outcomes between the intervention and control arms with Poisson regression using arm assignment as the primary model term. Regressions will control for age, sex, race/ethnicity, and each prior baseline outcome (e.g., for the DAOH-120 primary outcome, model will control for DAOH in the 120 days prior to randomization).

The randomization will be balanced on the primary outcome.

Power

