The cost prediction model will identify approximately 500 patients each month, who will undergo a 1:1 randomization stratified on DAOH over the 120 days prior to randomization to either the intervention or control arms. The investigators will enroll patients for 10 months, accruing approximately 5000 patients. On an intention-to-treat basis, two groups of 2,500 patients would provide 80% power to detect an effect size of 0.08 standard deviations (SD) on our primary outcome, DAOH, assuming a two-sample t-test and a two-sided 0.05 significance level. Assuming that only 25% of intervention patients contacted actually enroll in the complex care management program, this study would be adequately powered to detect an effect size as small as 0.32 SDs on the primary outcome.

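### The primary DAOH-120 model uses only 120 days of utilization history; adding the longer-window counts implied by the secondary models is a small, optional gain in precision

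*SAP*

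**What the plan says.** The primary outcome is "Days alive and out of hospital (DAOH) at 120 days from randomization". The Analysis plan section gives one covariate rule for every outcome: "Regressions will control for age, sex, race/ethnicity, and each prior baseline outcome". Its only illustration is the primary model: "for the DAOH-120 primary outcome, model will control for DAOH in the 120 days prior to randomization". The Power section makes that same prior 120-day DAOH the stratifier for randomization, so no other utilization history enters the stratification or, on the example, the primary analysis.

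The Secondary Outcomes list includes a longer-window version of the primary measure, "Days alive and out of hospital (DAOH) at 10 months from randomization". Among its event counts is "All-cause hospitalizations at 10 months from randomization"; spending and ED use are also followed for 10 months. If the rule treats these as it treats the primary outcome, each needs a baseline value over a matched window. The SAP does not state how long those look-backs are.

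The model is a Poisson regression with arm as the main term. No variance estimator is named. The sample size rests on an unadjusted two-sample t-test with "80% power to detect an effect size of 0.08 standard deviations (SD) on our primary outcome".

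**The concern.** Everyone is alive at randomization, so prior 120-day DAOH is simply 120 minus days in hospital. All patients without an admission in that window take the value 120. The covariate distinguishes them as a group from recently admitted patients, but it cannot rank them among themselves. A patient with three admissions five to nine months ago looks the same as one with none.

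Longer-window counts of admissions and ED visits would separate some of these patients. If they are built anyway for the 10-month models, leaving them out of the primary model gives up some precision. What is at stake is the width of the interval for the primary comparison, not its validity. The Power section plans for a small intention-to-treat effect and assumes that only 25% of contacted intervention patients enroll, so a modest gain is worth having if it is nearly free.

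**Working it through.** **1. The plan's own figure.** Inputs from the Power section: 2,500 per arm, effect 0.08 SD, two-sided 0.05, two-sample t-test.

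- Power: 0.08 / sqrt(2/2500) = 0.08 / 0.02828 = 2.828; 2.828 − 1.960 = 0.868, which gives 80.7%.
- Required size: 2 × (1.960 + 0.842)² / 0.08² gives 2,453 per arm.
- Detectable effect at exactly 80% power: 2.802 × 0.02828 = 0.0792 SD.

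The stated 80% reproduces. It takes no credit for covariates, so nothing below changes it.

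**2. What extra covariates do.** Let R²₁ be the variance of DAOH-120 explained by the reference covariates and R²₂ the variance explained with the extra terms.

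- Fall in residual variance = 1 − (1 − R²₂)/(1 − R²₁).
- Equivalent extra patients = 5,000 × [(1 − R²₁)/(1 − R²₂) − 1].

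**3. Size, by simulation.** The SAP gives no R², so every input here is assumed. There were 300,000 simulated patients per scenario. A gamma frailty is shared by admissions before and after randomization (lognormal stay, mean 6 days), ED visits (1.5 per year) and death (risk proportional to frailty^0.7). R²₁ is for prior 120-day DAOH alone; R²₂ adds log(1 + admissions) and log(1 + ED visits) over 10 months.

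| Admissions/yr | Frailty shape | 120-day deaths | R²₁ | R²₂ | Fall in residual variance | Equivalent patients |
|---|---|---|---|---|---|---|
| 0.8 | 1.5 | 3% | 0.003 | 0.017 | 1.4% | 71 |
| 1.5 | 1.5 | 3% | 0.010 | 0.037 | 2.7% | 140 |
| 0.8 | 0.7 | 3% | 0.012 | 0.048 | 3.6% | 189 |
| 1.5 | 0.7 | 6% | 0.033 | 0.089 | 5.8% | 307 |
| 1.5 | 0.7 | 3% | 0.034 | 0.094 | 6.2% | 331 |

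The last two columns use the rounded R² shown; unrounded values give 1.5-6.3% and about 74-335 patients. Between 65% and 80% of simulated patients tie at 120. Two repeat simulations gave 1.4-6.1% and 1.5-6.4%. Weakening the link to older utilization and selecting high-utilization patients, as a cost prediction model would, lowered the range to about 0.9-6%, or roughly 43-300 patients. Taken together: about 1-6%, roughly 40-335 patients.

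**4. In terms of power.** Taking the unadjusted 0.0792 SD as reference, a 0.9% fall multiplies the detectable effect by sqrt(0.991) = 0.995, giving 0.0789 SD. A 6.3% fall multiplies it by sqrt(0.937) = 0.968, giving 0.0767 SD. Power at 0.08 SD moves from 80.7% to about 81-83%.

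**5. A check without the simulation.** Assume that the planned covariates explain 10% of the variance and the extra terms a further 1-10%. Residual variance falls by 0.01/0.90 = 1.1% to 0.10/0.90 = 11.1%. Power at 0.08 SD rises from 84.6% to 85.0-88.5%, equivalent to a total of about 5,056-5,625 patients. If the extra terms explain nothing further, the gain is nil.

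**The case against.** The strongest reply is that nothing here is wrong. Adjusting for the outcome's own baseline value, which is also the stratifier, is standard and valid, and almost any plan could carry more prognostic covariates. That stands, and it sets the priority of the point.

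Several narrower objections also stand:

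- **The look-back is inferred.** A reader might conclude that the SAP requires 10 months of prior utilization for every patient and that these data are already assembled. It does not say so; the window is extrapolated from one example. The phrase about each prior baseline outcome could even mean that all baseline outcomes enter every model, although the example does not read that way.
- **The covariate is informative at its ceiling.** Having no admission in 120 days marks a lower-risk group. The weakness is only within that group, and age, sex and race/ethnicity can separate some of those patients.
- **The comparator is incomplete.** The simulation omits age, sex and race/ethnicity, so the gain over the full planned model is smaller than shown.
- **Constant frailty favors longer windows.** This is fair, but the gain persisted at a lower level when the link to older utilization was weakened and patients were selected for high utilization.
- **The variance estimator matters.** A model-based Poisson standard error depends on the fitted means and would hardly change. The gain appears only with a robust or dispersion-scaled variance, which the SAP does not name.

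What survives is a prespecified addition with a clear direction of benefit and very little cost.

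**Conclusion.** The point holds as a small missed efficiency. It is not an error or a contradiction. On the SAP's worked example, the primary model carries one utilization covariate, tied at 120 for everyone without a recent admission, while the covariate rule implies longer-window counts that could sharpen it. The likely benefit is a 1-6% fall in residual variance relative to prior 120-day DAOH alone, and less against the full planned model. It rests on assumed admission rates, frailty, length of stay and 3-6% mortality, and on treating linear-model R² as a guide to a Poisson model with robust standard errors.

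A reader might infer that the trial is underpowered or its primary analysis unsound without these terms. The document does not support that: the 80% power reproduces without any covariates, and the planned adjustment is valid. Larger gains from scenarios with no deaths should not be relied on, because the outcome counts days alive and mortality is itself a secondary outcome. The priority is optional.

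**What to change.** In the Analysis plan section, before outcomes are examined by arm:

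- State the look-back used for the baseline values of the 10-month outcomes.
- For the primary DAOH-120 model, keep age, sex, race/ethnicity and prior 120-day DAOH, and add log(1 + prior hospitalizations) and log(1 + prior ED visits) over that look-back. Log(1 + prior expenditures) may be added as well; it was not simulated, so no gain is claimed for it.
- Specify robust (sandwich) standard errors for the Poisson model, so that any gain appears in the reported interval.
- The DAOH-30 and DAOH-90 models may take the same terms while keeping their own matched baseline DAOH. No gain was calculated for them.
- Prior 10-month DAOH need not be added, because it contains the 120-day window and overlaps with the admission count.

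The cost is a few sentences in the SAP and two or three more coefficients with about 5,000 patients. No new data are needed, provided that the longer look-back is in fact built for the secondary models. Because all added terms are measured before randomization and fixed in advance, they introduce no bias into the intention-to-treat comparison.

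### Does the 0.32 SD in the power section misstate the effect that the trial can detect?

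*SAP*

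**What the plan says.** The Power section of the SAP expects about 500 patients a month for 10 months, randomized 1:1. By intention to treat, it states that the two arms give "80% power to detect an effect size of 0.08 standard deviations (SD) on our primary outcome". The calculation is for a t-test at the two-sided 5% level.

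The next sentence begins "Assuming that only 25% of intervention patients contacted actually enroll in the complex care management program" and concludes that "this study would be adequately powered to detect an effect size as small as 0.32 SDs on the primary outcome". It does not name the population to which 0.32 SD applies.

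Under Exploratory Outcomes, protocol fidelity is measured in both arms. For the intervention arm the measure is "the proportion of patients randomized to the intervention who enroll in the complex care management program". For controls it is the share, again of those randomized, who stay out of the program. The Analysis plan section compares outcomes by assigned arm. It plans no comparison restricted to enrollees.

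**The concern.** The two detectable effects differ fourfold, and both are described as effects on the primary outcome. A reader could take 0.32 SD as the arm difference that the trial can detect once uptake is low, and later judge the observed arm difference against 0.32 instead of 0.08. That would be a mistake, because the detectable arm difference depends on the numbers randomized and not on how many enroll.

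There is also a question of denominators. The dilution of an intention-to-treat effect depends on the share of all patients randomized to intervention who enroll, less any share of controls who enroll. The power sentence takes 25% of those contacted and gives no value for controls. The fidelity outcome counts patients randomized. If outreach misses some intervention patients, enrollment among those randomized falls below 25%. The 0.32 SD would then be optimistic, and the planning value could not be set directly against the fidelity result.

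**Working it through.** **Inputs from the SAP (Power):** 2,500 per arm, 1:1, two-sided 0.05, 80% power, two-sample t-test, 0.08 SD by intention to treat, 25% enrollment among those contacted, 0.32 SD. The SAP gives no contact rate and no assumed control enrollment.

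**1. The intention-to-treat figure.** By the normal approximation the sum of the z values is 1.960 + 0.842 = 2.802.
- Detectable difference: 2.802 × √(2/2500) = 0.079 SD.
- Patients needed for 0.08 SD: 2 × (2.802/0.08)² ≈ 2,453 per arm.
- Power at 0.08 SD with 2,500 per arm: 80.7%; the exact t-test calculation also gives 80.7%.

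The plan's 0.08 SD is reproduced.

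**2. What 0.32 SD can mean.**
- *A difference between arms.* This would need only 2 × (2.802/0.32)² = 153.3, so 154 per arm. With 2,500 per arm the power would be practically 100%. It does not fit.
- *A direct comparison using enrollees only.* Enrollees number 0.25 × 2,500 = 625. Against 2,500 controls the detectable effect is 2.802 × √(1/625 + 1/2500) = 0.125 SD; against 625 controls it is 2.802 × √(2/625) = 0.158 SD. Neither fits.
- *An effect among enrollees, diluted over the whole arm.* 0.08/0.25 = 0.32 SD, an exact match (0.317 from the unrounded 0.0792).

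Only the third reading returns the figure. It requires that 25% of all patients randomized to intervention enroll, that no controls enroll, and that non-enrollees are unaffected.

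**3. Sensitivity to the unstated inputs.** Let c be the share of intervention patients contacted and p the share of controls who enroll. The enrollee effect matching 0.08 SD is 0.08/(0.25c − p). The values of c and p below are assumptions.

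| c | p | Enrollee effect (SD) | Power for a true enrollee effect of 0.32 SD |
|---|---|---|---|
| 1.0 | 0 | 0.32 | 81% |
| 0.9 | 0 | 0.36 | 72% |
| 0.8 | 0 | 0.40 | 62% |
| 0.5 | 0 | 0.64 | 29% |
| 1.0 | 0.02 | 0.35 | 74% |
| 1.0 | 0.05 | 0.40 | 62% |

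The intention-to-treat detectable effect is 0.08 SD in every row.

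**4. What depends on 0.32 SD.** The total comes from expected accrual, 500 × 10 = 5,000, and not from 0.32. The planned models use assigned arm as the main term. No test, analysis set or decision rule in the SAP takes 0.32 SD as an input.

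**The case for a change.** The strongest case for a change is that the sentence states a best case without its conditions. The phrase *as small as* holds only with essentially full contact and no control enrollment, and the SAP states neither. Inferring that the figure refers to enrollees does not tell the reader whether 25% of those contacted equals 25% of those randomized. The plan itself treats control enrollment as something to monitor. The repair would cost one sentence.

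Much of this stands as description. The word enrollees is absent, contacted is not the same as randomized, and the table shows that the enrollee figure is sensitive to both unstated inputs.

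It does not amount to an error, for three reasons. First, the contrast is already on the page: one figure is tagged intention-to-treat, and the next is introduced by partial enrollment and is exactly four times as large at one-quarter uptake. Second, non-enrollment of controls counts as fidelity, so zero control enrollment is evidently the intended design. Third, whether every intervention patient is contacted is an outreach procedure that would normally be described in the protocol, which was not available. If contact is attempted for the whole arm, the two denominators coincide. A rewording that put 25% of all randomized patients into the sentence would assert something that the SAP does not state.

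**Conclusion.** No change to the plan follows. The 0.08 SD is correct on the SAP's stated inputs (0.079 SD at 80% power; 80.7% power at 0.08 SD). The 0.32 SD is correct as the corresponding effect among enrollees, given 25% enrollment of those randomized, no control enrollment and no effect in non-enrollees. What is missing is a label, which a statistical reader supplies from the context.

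The denominator point is conditional. If contact is incomplete or some controls enroll, 0.32 SD understates the enrollee effect needed, for example 0.40 SD at an assumed 80% contact or an assumed 5% control enrollment. Rewording would not alter that exposure. The fidelity outcome already records enrollment per patient randomized in both arms, so the conversion can be redone with observed values. The sample size, the intention-to-treat power statement and the comparison by assigned arm stand in every case. If the sponsor edits the section for other reasons, naming enrollees as the population would be a courtesy to readers; it would not improve the trial's result.
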